#### 5.3 Work Package 3 - Realist evaluation

#### Study design

Mixed methods case study Realist Evaluation of FCP in primary care. To assess the clinical and costeffectiveness of FCP service delivery models and non-FCP physiotherapy provision, we will recruit patients within GP practices who are actively undergoing physiotherapy management for a current MSKD and collect longitudinal data over a 6 month period. Each case study will also combine qualitative interviews with key stakeholders guided by pre-determined programme theories.

### Case study sampling and recruitment

Sampling: We require 39 case study sites across the UK, representing key sampling criteria (e.g. geographical location) that are likely to impact on service delivery. Case study sites will be sub-categorised into three strands:

- i. FCP (n=13)
- ii. FCP has additional qualifications [FCPAQ] (i.e. non-medical prescribing, injecting) (n=13)
- iii. No FCP service is available, physiotherapy provision via a different pathway [PT] (n=13)

In order to achieve a wide geographical sample, case study sites will be selected from England, Wales, Scotland and Northern Ireland. Amongst these, we will also ensure a range of urban and rural environments are included, and a range of sample deprivation based on GP population postcode deprivation index.

We will also record the duration that the service has been established as embeddedness is likely to impact on service outcomes. These will not be selection criteria for the sampling matrix, but the impact of service duration will be explored qualitatively.

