The research will be conducted in four work-packages (WP):

- 1. A UK-wide survey scoping exercise to identify key aspects of service provision. This will facilitate purposive sampling of delivery models (case studies) that will be subject to further in-depth investigation.
- A rapid realist review of identified aspects of service provision, derived from the scoping exercise, to
  establish the initial set of realist programme theories underpinning FCP models of care. This will be
  followed by a consensus exercise with key stakeholders to validate the programme theories, in terms
  of the resource-response mechanisms in various contexts (context-mechanism-outcome
  configurations).

- 3. In depth case study of three key delivery models (FCP; FCP with additional qualifications [FCPAQ], which for the purposes of this study is defined as the ability to prescribe and inject; and usual GP care), each at four different general practices (sites), using realist evaluation to examine outcomes. Data will be collected (quantitative and qualitative) on what works, for whom, how and in what circumstances, accounting for aspects of the context that have causal impact: (e.g. privately employed or federated, practice size, deprivation), and at what cost. Realist qualitative interviews will be conducted with five stakeholder groups involved in service provision across sites: (i) clinic receptionists; (ii) GPs; (iii) physiotherapists; (iv) patients; and (v) commissioners. Patients (n=580) attending with MSKD, will be followed for 6 months to track changes in pain and functioning using the SF36-Physical Component Summary (primary outcome measure), and compared across the care models. Secondary outcomes will include mental health, patient safety, time off work/change of work practices, health related quality of life and patient satisfaction, and will be collected with validated outcome measures. The scope of the economic evaluation will be informed by the realist programme theories to determine the costs and cost effectiveness given a range of associated processes, contexts, and outcomes.

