### Recruitment

In a previous work-package (WP1) we compiled a database of FCP practice sites who have expressed an interest in participating in this stage of the research. We will categorise these respondents according to the sampling criteria presented above, and using an off-site random allocation service will randomly select sites to approach. When there is only one matched case study site to the sampling criteria, we will approach that site only. We are confident that we can recruit sufficient sites from our survey return but will also approach the NIHR local Clinical Research Network (CRN) for support in recruitment of sites as required.

Thirteen case study sites that do not provide FCP services (PT) are also required; these sites will be recruited through the CRN according to the previously described criteria.

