Primary Outcome analysis: The change in SF-36 Physical Component Score from baseline to 3 months and from baseline to 6 months will be compared between the three service models using a 1-way analysis of variance. If a significant difference is seen, post-hoc unpaired t-tests comparing each pair of service models will be performed in order to determine the superior service model(s). Further comparisons of the three service models will be undertaken in the context of stepwise linear regression modelling, incorporating the demographic and clinical features of the patients, including their baseline SF-36 Physical Component Score. Dummy variables may also be included to represent individual sites. Regression analyses will include multilevel modelling in the form of a general linear mixed model with site as a random effect.

Secondary Outcomes analysis: The change in SF-36 Mental Health Score and in EQ5D-5L Health Related Quality of Life from baseline to 3 months and from baseline to 6 months will be compared between the three service models using a 1-way analysis of variance. If a significant difference is seen, post-hoc unpaired t-tests comparing each pair of service models will be performed in order to determine the superior service model(s).

A similar analysis will be performed for the Roland-Morris Disability Questionnaire score (for LBP patients only) due to the high prevalence and consultation rates for this disorder, for the General Practice Assessment Questionnaire (7, 9-10). For each of the three service models, the proportion of off work patients at baseline who reported having returned to work at 6 months will be compared using a chi-squared test. Costs analysis: Comparisons of costs between the 3 service models will be performed using appropriate statistical tests (according to the distributions of the relevant cost variables).

Health Economics analysis: Initially, we will conduct an analysis of the practice workforce team, and secondly a patient level analysis of outcomes for the sample of MSK patients recruited to the study will be undertaken.

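### The three strands need not have a similar mix of practice settings and the analysis names no practice-level covariate, so service model can be confounded with setting

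*Protocol*

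**What the plan says.** **Site selection (Protocol 5.3, Case study sampling and recruitment).** The protocol seeks 39 practices, 13 in each of three strands defined by the service the practice already offers: FCP, FCPAQ, or no FCP. On nation, "case study sites will be selected from England, Wales, Scotland and Northern Ireland". On setting, "Amongst these, we will also ensure a range of urban and rural environments are included, and a range of sample deprivation". The section expects its sampling criteria to affect service delivery and refers to a sampling matrix. It states no distribution for any one strand.

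**Route into the study (Protocol 5.3, site Recruitment).** For the FCP strands, "we compiled a database of FCP practice sites who have expressed an interest in participating in this stage of the research". These respondents are sorted by the criteria and sites to approach are picked at random, with the rule that "When there is only one matched case study site to the sampling criteria, we will approach that site only". For the 13 non-FCP practices, "these sites will be recruited through the CRN according to the previously described criteria".

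**Analysis (Protocol 5.3, Data analysis, Primary Outcome analysis).** Change in SF-36 PCS "will be compared between the three service models using a 1-way analysis of variance", followed by unpaired t-tests if significant. Further comparisons use stepwise regression "incorporating the demographic and clinical features of the patients", including baseline PCS. Site dummies are optional, and a mixed model has site as a random effect.

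**Sample size section.** The aim is non-inferiority with a margin of 2 SF-36 units. The section also suggests that 13 centres be randomised to each model.

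**The concern.** This is an observational comparison of practices that already run different services. Under the sampling rules, variety across the 39 sites would be satisfied even if the rural or more deprived practices fell mainly in one strand. Separate recruitment routes could make such a pattern more likely than chance would.

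If setting affects PCS change, the difference between models then mixes the effect of the service with the effect of where it is delivered. Neither the analysis of variance nor the t-tests adjust for anything. A site random intercept allows for the similarity of patients within a practice, but it does not remove a systematic difference between strands. With a margin of 2 units, a bias of a few tenths of a unit materially changes the chance of concluding non-inferiority.

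**Working it through.** **1. The plan's own figures reproduce.** Inputs from the Sample size section: margin 2, SD 6.5, one-sided 5%, power 80%, cluster size 14, ICC 0.0075, attrition 20%.
- Subjects per arm before clustering: 131 by the normal formula, 132 by the t-based calculation (stated 132).
- Design effect: 1 + 13 × 0.0075 = 1.0975, and 132 × 1.0975 = 144.9, so 145 per arm (stated 145).
- Attrition: 145 / 0.8 = 181.25 (stated 181); 13 × 14 = 182.
- Standard error of a difference between two arms: 6.5 × √(2/132) = 0.80. With 145 per arm and the design effect, 6.5 × √(2 × 1.0975/145) is also 0.80.

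**2. Room for a practice factor under the plan's ICC.** Between-practice SD = √0.0075 × 6.5 = 0.563. Suppose one binary factor, present in half of practices, explains a share *s* of between-practice variance. Practices with and without it then differ by d = 2 × 0.563 × √s. The shares are assumptions, since the documents give none.

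**3. A four-site gap between two strands of 13.** Bias = (4/13) × d. Power if the bias is against FCP = Φ((2 − bias)/0.80 − 1.645). One-sided error at the margin if it favours FCP = Φ(bias/0.80 − 1.645).

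| Share of between-practice variance | d | Bias | Power (80% unbiased) | Error (5% unbiased) |
|---|---|---|---|---|
| All | 1.13 | 0.35 | about 66% | about 11% |
| Half | 0.80 | 0.24 | about 71% | about 9% |
| A quarter | 0.56 | 0.17 | about 74% | about 8% |

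**4. How often chance alone would produce such a gap.** For two independent Binomial(13, 0.5) counts, a difference of four or more has probability 0.169 and of five or more 0.076. If only 30% of practices have the factor, these are 0.132 and 0.052; at 20%, 0.083 and 0.026. These are probabilities with no balancing at all, for one factor and one pair of strands.

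**5. Whether the planned site terms help.** Each practice has exactly one model, so the 13 site indicators in a strand add up to that strand's indicator. A design matrix of 39 site indicators has rank 39, and adding the three model indicators leaves it at 39. The model effect cannot be estimated beside a full set of site dummies. The site random effect can be fitted, but it leaves the bias in step 3 in place.

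**The case against.** **The same criteria govern every strand.** This stands. The non-FCP practices are recruited to the same list, there is a sampling matrix, and the rule for a single matching site is consistent with filling cells. A reader might infer that comparators are chosen without regard to setting, but the text does not support that. What is missing is a requirement that the mix be similar by strand. The word matched in the site Recruitment section means matched to the criteria, not to an FCP practice.

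**Realist evaluation wants variation in context.** It does, and one-to-one matching would work against that aim. Thirteen comparators could not be paired with 26 FCP and FCPAQ sites in any case. Balancing frequencies keeps the variation and spreads it over the strands, which the stated non-inferiority aim needs.

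**Covariates belong in the SAP.** Partly true. The regression wording does not exclude practice factors, and patient demographics may capture some deprivation. But the protocol already fixes an unadjusted first comparison and describes the covariates as patient features. Site selection cannot be repaired later: if strands scarcely overlap on a factor, adjustment cannot recover the comparison.

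**The Summary already commits to adjustment.** It speaks of "accounting for aspects of the context that have causal impact", with practice size and deprivation among its examples, and one might read the regression as breaking that promise. The sentence concerns quantitative and qualitative data collection for the realist evaluation as a whole, so it is not a commitment about this model.

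**The ICC is very small.** This also stands, and it limits the bias. A 2-point difference on a 50:50 factor would imply a between-practice SD of 1 and an ICC of 1/6.5² = 0.024, above the plan's 0.0075. Larger effects are therefore not used here.

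**Conclusion.** The concern holds as a missing balance requirement combined with an analysis that names no practice-level factor. On the plan's SD and ICC, a four-site gap on one 50:50 factor would shift the contrast by 0.17 to 0.35 PCS units. That costs about 6 to 14 points of power, or adds about 3 to 6 points to the one-sided error, according to direction. The upper end needs a single factor to account for all between-practice variance.

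These are illustrations. The effect of setting on PCS and the actual mix by strand are not in the documents, so the true bias cannot be derived. A reader might conclude that the comparison is biased, or biased towards FCP, but nothing in the text shows either.

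A reader might also take the Sample size section to mean that randomisation protects the comparison. It does not: under the sampling and recruitment sections, practices enter a strand by the service they already run, and the random step only selects which interested FCP sites to approach.

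**What to change.** **Case study sampling and recruitment, and site Recruitment.** Apply the sampling matrix within each strand, so that the three strands have a similar mix of nation, urban/rural status and deprivation band. This is frequency balance, not one-to-one matching. Select the FCP and FCPAQ sites to a common distribution, then ask the CRN for non-FCP practices that mirror it.

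**Data analysis, Primary Outcome analysis.** Base the main between-model comparison on the mixed model instead of the unadjusted analysis of variance. Include site as a random effect, and baseline PCS, urban/rural status and practice deprivation as fixed effects, with nation where numbers allow. Drop the site dummies.

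**Sample size.** Reconcile the statement that centres are randomised to models with the sections that select practices by existing service.

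**Cost.** A more specific request to the CRN, possibly slower site identification, and a few between-site degrees of freedom. Of 39 − 3 = 36, one goes to urban/rural status and one to deprivation if entered as a single term, leaving 34, or 31 if nation is added. Urban/rural status, deprivation and nation have to be known for sampling anyway. Unmeasured differences, such as those tied to a practice's choice to offer FCP, would remain and should be acknowledged.

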### Recruitment

In a previous work-package (WP1) we compiled a database of FCP practice sites who have expressed an interest in participating in this stage of the research. We will categorise these respondents according to the sampling criteria presented above, and using an off-site random allocation service will randomly select sites to approach. When there is only one matched case study site to the sampling criteria, we will approach that site only. We are confident that we can recruit sufficient sites from our survey return but will also approach the NIHR local Clinical Research Network (CRN) for support in recruitment of sites as required.

Thirteen case study sites that do not provide FCP services (PT) are also required; these sites will be recruited through the CRN according to the previously described criteria.

### **Quantitative Design**

We will recruit a consecutive longitudinal sample per practice case study, to measure clinical outcomes and resource utilisation over a six-month period with patients consulting with MSKD. Analysis will determine clinical and cost-effectiveness of FCP and non-FCP services, and identification of patient satisfaction and any safety concerns regarding models of care.

#### **Inclusion Criteria**

- (i) Patients consulting with a suspected MSKD episode, defined as any acute or chronic disorder related to the spinal or peripheral musculoskeletal system;
- (ii) Not consulted for the same problem in preceding 3 months;
- (iii) 18 years and over;

(iv) Willing to provide informed consent for healthcare records to be viewed by specified members of the research team for the purpose of this study.

#### **Exclusion Criteria**

- (i) Under 18 years of age;
- (ii) Receiving palliative care for a terminal illness;
- (iii) If non-English speaking and unwilling to provide informed consent and communicate through an interpreter;
- (iv) Unwilling to provide informed consent for healthcare records to be viewed by specified members of the research team for the purpose of this study.

### Recruitment

[figure not shown]
All patients attending their GP practice consulting with an MSKD and meeting the study criteria will be eligible to participate.

In practices with FCP, all new patients consulting the physiotherapist will be provided with a participant information pack by their treating physiotherapist. This pack will include an information sheet explaining the study, contact details of the study team and a consent form with return envelope. Potential participants who require further information will be encouraged to contact the study team to discuss participation. If eligible and willing to participate, they will be required to return the signed consent form to the study team. On receipt of this form, we will contact the potential participant to confirm eligibility, and if eligible will complete the health economics questionnaire (CSRI) over the phone. We will then send a set of outcome measures with a return envelope for completion by the participant. At the participants request we can also provide the outcome measures via email for electronic completion. We will track the number of packs distributed and collect basic anonymised demographic data for all approached patients, enabling us to calculate recruitment rates and report the profile of non-participants. At the end of the data collection period we will also work with database managers in FCP practices to determine the amount of patients who continued to consult their GP for MSKD rather than the FCP, so we can present a descriptive analysis of service engagement. See figure 1.

When the patient consults, the physiotherapist also has the option to provide a recruitment pack and ask whether the patient would like a member of the study team to contact them to explain the study further. For those who would like that, the patient verbally consents to their name and telephone number only being passed to the study team. This will be managed from .nhs to .nhs secure email. The telephone call will simply include further detailing of the study after which the patient can determine whether they would like to participate.

We will monitor recruitment within each study site to ensure even distribution across sites. Where recruitment is slow because packs are not being distributed, we will visit practices to discuss how this process could be best facilitated. Where recruitment is limited due to patient uptake, we have sufficient time to extend the recruitment period for a maximum of 6 weeks to facilitate the process. We will also where possible advertise the study within the practice, encouraging patients to request an information pack.

[figure not shown]
Figure 1 below shows participant throughput in FCP practices

For GP practices that do not have a FCP model, we will provide study information packs to GP surgeries and request GPs or reception staff to distribute to individuals consulting with an MSKD based on the preference of the individual practice. As above, when the patient consults, practice staff also have the option to provide a recruitment pack and ask whether the patient would like a member of the study team to contact them to explain the study further. For those who would like that, the patient verbally consents to their name and telephone number only being passed to the study team. This will be managed from .nhs to .nhs secure email. The telephone call will simply include further detailing of the study after which the patient can determine whether they would like to participate.

We will track the number of packs distributed to recruit the required sample size to provide us with information on recruitment rates. This pack will include an information sheet explaining the study, contact details of the study team and a consent form with return envelope. Potential participants who require further information will be encouraged to contact the study team to discuss participation. If eligible and willing to participate, they will be required to return the signed consent form to the study team. On receipt of this form, we will contact the potential participant to confirm eligibility, and if eligible will complete the health economics questionnaire (CSRI) over the phone. We will then send a set of outcome measures with a return envelope for completion by the participant. At the participants request we can also provide the outcome measures via email for electronic completion. At the end of the data collection period we will also work with database managers to determine the amount of patients who consulted their GP for MSKD, so we can present a descriptive analysis of service use. See figure 2.

Figure 2 below shows participant throughput in non-FCP practices

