### Sample size

The aim of this research is to determine that FCP is not substantially worse (non-inferiority analysis) than GP based practice. For the purpose of assay sensitivity, the study is designed as a three arm design which includes usual GP care, FCP and FCPAQ. This sample size computation also accounts for the similarities of patients within each GP centre and treats each GP centre as a cluster within which patients are nested.

Based on Bishop et al (36) a non-inferiority margin of 2 units in SF-36 scale, that is the standard practice is either superior or worse no more than by 2 unit is assumed. Previous research in MSKD, such as Angst et al. (45) has estimated a minimal clinically important difference from 4 points for the SF-36v.2 PCS subscale. The standard deviation of the difference between the SF-36 score between models are assumed to be 6.5 based on Salisbury et al (7). In a one sided 0.05 significance non inferior hypothesis test, to achieve 80% power, 132 subjects are required. To account for the hierarchical nature of the design, i.e. patients are nested within GP centres, this number should be inflated by the design effect.

The design effect for a cluster size of 14 and an intra cluster correlation coefficient (ICC) of 0.0075 (29) will be 1.09, requiring a total sample size to 145 per arm. After allowing for attrition of 20%, the total subjects required per arm is increased up to 181, making the total of at least 13 GP centres per arm, and a per practice sample size of approximately n=14.

It is suggested to randomise 13 GP centres to each physio model and recruit 14 patients with MSKD within each GP centre. In our pilot study, 814 patients consulted with MSKD over 6 months (practice population ~6200). Similar studies in primary care (7, 36) report estimates of 40% of consulting patients being eligible and consenting, we are confident in recruiting the required sample, enabling comparisons between sites and models.

In the analysis, GP centres are included as a random effects in a General Linear Mixed model to account for similarity of patients within each GP centre. The sample size computation was performed using a combination of nQuery 8 and SAS version 9.4 software.

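### The recruitment routes enrol physiotherapist-seen patients at FCP and FCPAQ sites but general MSKD consulters at non-FCP sites, and the protocol's statements of the study population conflict

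*Protocol*

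**What the plan says.** All references are to the Protocol.

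- **Eligibility.** The patient Recruitment text in section 5.3 makes anyone attending the practice with an MSKD eligible if the study criteria are met. Inclusion criterion (ii) requires no consultation for the same problem in the previous 3 months.
- **FCP and FCPAQ sites.** "In practices with FCP, all new patients consulting the physiotherapist will be provided with a participant information pack by their treating physiotherapist". MSKD patients who still see the GP are counted from the practice database at the end, for description only.
- **Non-FCP sites.** The study team will "request GPs or reception staff to distribute to individuals consulting with an MSKD based on the preference of the individual practice". No contact with a physiotherapist is required.
- **Study design paragraph, all models together.** "we will recruit patients within GP practices who are actively undergoing physiotherapy management for a current MSKD".
- **Comparator label.** Case study sampling describes the third strand as "No FCP service is available, physiotherapy provision via a different pathway [PT"]. The Sample size section has a "three arm design which includes usual GP care, FCP and FCPAQ", and the Summary and section 5 also name usual GP care.
- **Information on those approached.** The FCP route will "collect basic anonymised demographic data for all approached patients, enabling us to calculate recruitment rates and report the profile of non-participants". The non-FCP route says: "We will track the number of packs distributed to recruit the required sample size to provide us with information on recruitment rates".
- **Analysis.** The Primary Outcome analysis starts with a one-way ANOVA of change in SF-36 PCS followed by t-tests. Baseline PCS and patient features enter in further stepwise regression, and site enters as a random effect in a mixed model.

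**The concern.** A patient reaches the FCP cohort by being routed to the physiotherapist and accepting that route. A comparator patient needs only to consult with an MSKD and be handed a pack. The arms may then differ in case mix before any effect of the service model, and the difference is built in at enrolment.

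This matters because the stated aim is non-inferiority within 2 PCS points, so a modest shift can change the conclusion. The same patients supply the cost-effectiveness and cost-utility analyses.

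The conflicting definitions add a second problem. Someone already under physiotherapy, a new MSKD consulter and a recipient of usual GP care are not the same person. A site following one paragraph would recruit differently from a site following another.

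**Working it through.** **1. The population statements side by side**

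| Place in section 5.3 | Who is described | Applies to |
|---|---|---|
| Recruitment, opening | Any MSKD consulter meeting the criteria | All arms |
| Recruitment, FCP route | New patients seen by the physiotherapist | FCP, FCPAQ |
| Recruitment, non-FCP route | MSKD consulters given a pack by GP or receptionist | Comparator |
| Study design | Patients already under physiotherapy | All arms |
| Inclusion criterion (ii) | No visit for this problem in the last 3 months | All arms |

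The FCP route is narrower than the opening statement. The non-FCP route is close to it, subject to each practice's way of distributing packs. The Study design definition can fit the FCP route, because a new FCP patient enters physiotherapy at that visit. It does not fit the non-FCP route, which requires no physiotherapy. It also sits badly with criterion (ii) where physiotherapy is reached through an earlier GP visit.

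**2. The plan's own sample size**

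Inputs from the Sample size section: margin 2, SD 6.5, one-sided alpha 0.05, power 0.80, cluster size 14, ICC 0.0075, attrition 20%. A true difference of 0 is assumed.

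- n per arm = 2 × 6.5² × (1.645 + 0.842)² / 2² ≈ 131, against 132 stated.
- Design effect = 1 + 13 × 0.0075 = 1.0975 (stated as 1.09). 132 × 1.0975 = 144.9, so 145.
- 145 / 0.80 = 181.25, stated as 181. The planned 13 × 14 gives 182.

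The size is reproduced within rounding. It leaves no room for a selection difference between arms.

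**3. Effect of an assumed bias b (illustration)**

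With an effective 132 per arm, SE = 6.5 × √(2/132) = 0.80.

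- Type I error at a true deficit of 2, bias favouring FCP: 1 − Φ(1.645 − b/SE).
- Power at a true difference of 0, bias against FCP: Φ((2 − b)/SE − 1.645).

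| b (points) | Type I error, towards FCP | Power, against FCP |
|---|---|---|
| 0 | 0.050 | 0.804 |
| 0.25 | 0.091 | 0.706 |
| 0.5 | 0.154 | 0.591 |
| 1.0 | 0.346 | 0.346 |

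For b = 0.5: 0.5/0.80 = 0.625 and 1 − Φ(1.020) = 0.154. On the other side, 1.5/0.80 = 1.875 and Φ(0.230) = 0.591.

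**4. How such a bias could arise**

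Let s be the share of MSKD consulters who would see the FCP, and D the gap in mean PCS change between them and those who stay with the GP. If the comparator contains both kinds, b ≈ (1 − s) × D. For example, s = 0.5 and D = 1 give 0.5 points. The document gives neither s nor D, and D may have either sign.

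**The case against.** Several stronger readings are tempting, and the document does not support them.

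- **That the comparator is described as patients already under physiotherapy.** The Study design sentence covers FCP and non-FCP provision together. It is an outlying sentence that conflicts with other text, not a definition of one arm.
- **That FCP sites can enrol only physiotherapist-seen patients and comparator sites enrol everyone.** Practice advertising lets a GP-seen patient ask for a pack, though nothing makes this systematic. Comparator packs go out as each practice prefers, so an all-comer sample is not assured there either.
- **That selection in the comparator cannot be checked.** Data analysis tabulates eligible, approached and agreeing numbers by site and for all three models, and non-FCP MSKD consulters are counted. Only the profile of approached patients is unstated on that side.
- **That the bias favours FCP.** The Background says it is unclear whether non-physician assessment serves complex patients well. It does not say that they stay with the GP. Patients who stay could have milder problems, and staff discretion could keep complex patients out of the comparator. A worse baseline need not mean a smaller change.
- **That the bias could use up the whole margin.** That needs assumed values at the top of both ranges, for example half of patients not routed to the FCP and a 4-point gap: 0.5 × 4 = 2.

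The plan also has real mitigation. Group features are compared before outcomes, and later models adjust for baseline PCS and patient features with site as a random effect. This stands, but it is partial. The first comparison is unadjusted, and covariates cannot capture unmeasured reasons for routing. The word randomise in the Sample size section does not help, because sites are sampled by the model they already run.

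**Conclusion.** The concern holds. The routes sample different groups, the population statements conflict, and neither site selection nor the first primary comparison protects against the resulting bias. The bias could run in either direction, and its size cannot be estimated from the document.

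The illustration shows only that the design is sensitive. An assumed 0.5 points, a quarter of the margin, takes one-sided type I error to about 0.15, or power to about 0.59, depending on direction. It rests on SD 6.5, an effective 132 per arm, a normal approximation and no covariate adjustment. The sample size arithmetic itself is sound.

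**What to change.** 1. State one target population: adults newly consulting the practice with an MSKD. Delete or correct the sentence about patients already under physiotherapy. Reconcile Study design, Case study sampling, Inclusion Criteria, both recruitment routes and Sample size, including the comparator's name.
2. Use the same entry point in all arms, for example packs offered at booking to consecutive new MSKD consulters, whoever sees them. Otherwise say explicitly that the FCP estimate applies to FCP-seen patients only.
3. Collect the same anonymised demographics of approached patients at non-FCP sites.
4. Make the mixed model the primary comparison instead of the unadjusted ANOVA, with baseline PCS, pre-specified patient features and site as a random effect.

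**Cost.** A small amendment and a slightly longer log at 13 sites. If enrolment moves to booking, some FCP-site participants will be GP-seen, which dilutes the contrast between models.

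**A remedy to avoid as primary.** One could restrict the comparator to patients judged bookable with an FCP. The protocol describes no common triage list. The judgement would be unblinded and made in one arm only, and it leaves out patient acceptance. If half were not bookable, 182 × 0.5 = 91 enrolled and 91 × 0.8 ≈ 73 would complete. Dividing by 1.0975 gives about 66.5 effective patients, SE = 6.5 × √(1/132 + 1/66.5) ≈ 0.98, and power of about 66%. At most it could be a sensitivity analysis with common written criteria.
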